8.3 Recommended Binimetinib Dose Modifications

\rightarrow \rightarrow Use the NCI Common Terminology Criteria for Adverse Events (CTCAE) version 5.0* unless				
CTCAE	otherwise specified $\leftarrow \leftarrow$			
CTCAE System/Organ/Class (SOC)	ADVERSE EVENT	ACTION**		
	BASED ON INTE	RVAL ADVERSE EVENT		
Eye Disorders	Retinopathy and Retinal detachment			
	Grade 2 or above	 Withhold binimetinib for up to 10 days. If improves and becomes asymptomatic, resume at the same dose. If not improved, resume at a lower dose level or permanently discontinue binimetinib. 		
	Retinal Vein Occlusion (RVO)			
	Any Grade	Permanently discontinue binimetinib.		
	Eye disorders-Other, specify			
	Grade 1-2	Maintain dose level of encorafenib and binimetinib and increase frequency of ophthalmic monitoring to at least every 14 days until stabilization or resolution.		
	Grade 3	Interrupt dosing of encorafenib and binimetinib and refer patient to ophthalmologist within 7 days.		
		 If resolved to Grade ≤ 1 in ≤ 21 days, resume treatment at 1 reduced dose level of encorafenib and binimetinib. 		
		 If not resolved to Grade ≤ 1 in ≤ 21 days, permanently discontinue encorafenib and binimetinib and close follow-up with ophthalmic monitoring until stabilization or resolution. 		

\rightarrow \rightarrow Use the NCI Common Terminology Criteria for Adverse Events (CTCAE) version 5.0* unless otherwise specified $\leftarrow \leftarrow$			
CTCAE System/Organ/Class (SOC)	ADVERSE EVENT	ACTION**	
	Grade 4	Permanently discontinue encorafenib and binimetinib and immediate follow-up with ophthalmic monitoring until stabilization or resolution.	
	Uveitis		
	Grade 1-3	 If Grade 1 or 2 does not respond to specific ocular therapy, or for Grade 3 uveitis, withhold binimetinib and encorafenib for up to 6 weeks. If improved, resume at same or reduced dose. 	
		If not improved, permanently discontinue binimetinib.	
	Grade 4	Permanently discontinue encorafenib and binimetinib.	
Cardiac Disorders	Heart Failure and Left ventricular systolic dysfunction		
	Grade 1	Withhold binimetinib for up to 4 weeks, evaluate LVEF every 2 weeks. Resume binimetinib at a reduced dose if the following are present:	
		 LVEF is at or above the LLN and Absolute decrease from baseline is 10% or less and Patient is asymptomatic. If LVEF does not recover within 4 weeks permanently 	
		discontinue binimetinib.	
	Grade 3-4	Permanently discontinue binimetinib. Closely monitor LVEF until resolution or up to 16 weeks.	
Respiratory, thoracic and mediastinal	Pneumonitis, pulmonary fibrosis		
disorders	Grade 2	 Withhold binimetinib for up to 4 weeks. If improves to Grade 0-1, resume at a reduced dose. If not resolved within 4 weeks, permanently discontinue. 	
	Grade 3 or Grade 4	Permanently discontinue binimetinib.	
Investigations	Alanine aminotransferase or aspartate aminotransferase increased		

$\rightarrow \rightarrow$ Use the NCI C	Common Terminology Crit otherwise	eria for Adverse Events (CTCAE) version 5.0* unless e specified 🗲 🗲
CTCAE System/Organ/Class (SOC)	ADVERSE EVENT	ACTION**
	Grade 2	Maintain binimetinib dose.
		• If no improvement within 2 weeks, withhold binimetinib until improved to Grade 0-1 or to pretreatment/baseline levels and then resume at the same dose.
	Grade 3 or 4	See Other Adverse Reactions
	CPK increased	
Investigations	Grade 4 asymptomatic or Any Grade with symptoms or with renal impairment	 Withhold binimetinib dose for up to 4 weeks. If improved to Grade 0-1 resume at a reduced dose. If not resolved within 4 weeks, permanently discontinue binimetinib.
	Investigations-Other, specify	
	Recurrent Grade 2 or	Withhold for up to 4 weeks.
	First occurrence of any Grade 3	 If improves to Grade 0-1 or to pretreatment/baseline levels, resume at reduced dose. If no improvement, permanently discontinue encorafenib and binimetinib.
	First occurrence of any	Permanently discontinue or withhold for up to 4 weeks.
	Grade 4	 If improves to Grade 0-1 or to pretreatment/baseline levels, then resume at a reduced dose. If no improvement, permanently discontinue encorafenib and binimetinib.
	Recurrent Grade 3	Consider permanently discontinuing encorafenib and binimetinib.
	Recurrent Grade 4	Permanently discontinue.
Gastrointestinal	Nausea/Vomiting	
disorders	Grade 1-2	Maintain dose level of encorafenib and binimetinib. Promptly institute antiemetic measure.

\rightarrow \rightarrow Use the NCI Common Terminology Criteria for Adverse Events (CTCAE) version 5.0* unless otherwise specified \leftarrow		
CTCAE System/Organ/Class (SOC)	ADVERSE EVENT	ACTION**
	Grade 3	Interrupt dosing of encorafenib and binimetinib until resolved to Grade ≤ 1 . Then resume treatment as 1 reduced dose level of encorafenib. Resume treatment with binimetinib at the current dose if, in the judgement of the Investigator, the toxicity is considered to be unrelated to binimetinib, or at 1 reduced dose level.
		Note: Interrupt dosing of encoratenib and binimetinib for \geq Grade 3 vomiting or Grade 3 nausea only if the vomiting or nausea cannot be controlled with optimal antiemetics (as per local practice).
	Grade 4	Permanently discontinue encorafenib and binimetinib.
Skin and subcutaneous tissue disorders	Skin and subcutaneous tissue disorders-Other, specify	
	Grade 2	If no improvement within 2 weeks, withhold until Grade 0-1. Resume at same dose if first occurrence or reduce dose if recurrent.
	Grade 3	Withhold until Grade 0-1. Resume at same dose if first occurrence or reduce dose if recurrent.
	Grade 4	Permanently discontinue encorafenib and binimetinib.

****** Use the following to describe actions in the Action column:

- Modified=A modification indicates a change in dose level during the current cycle. However, if a • modification was issued after the last dose was received in the current cycle, the modification should be reported on the subsequent cycle. "Yes, planned" should be selected if the dose level was changed according to protocol guidelines (i.e. due to adverse events, lab values, etc.); "Yes, unplanned" should be selected if the dose level change was not a part of protocol guidelines (e.g. vacation, mistake, etc.). Held doses (including omissions and delays) should not be reported as modifications.
- Omitted=An omission indicates a dose was skipped and not made up, or that the drug was discontinued.
- Delayed=A delay indicates dose was postponed or not received when expected. •

9.0 **Ancillary Treatment/Supportive Care**

Г

- 9.1 Antiemetics may be used at the discretion of the attending physician.
- 9.2 Blood products and growth factors should be utilized as clinically warranted and following institutional policies and recommendations. The use of growth factors should follow published guidelines of the American Society of Clinical Oncology (ASCO), Recommendations for the Use of WBC Growth Factors: American Society of Clinical Oncology Clinical Practice Guideline Update. J Clin Oncol 2015;33:3199-3212.

- 9.3 Patients should receive full supportive care while on this study. This includes blood product support, antibiotic treatment, and treatment of other newly diagnosed or concurrent medical conditions. All blood products and concomitant medications such as antidiarrheals, analgesics, and/or antiemetics received from the first day of study treatment administration until 30 days after the final dose will be recorded in the medical records.
- 9.4 Diarrhea: This could be managed conservatively with loperamide. The recommended dose of loperamide is 4 mg at first onset, followed by 2 mg every 2-4 hours until diarrhea free (maximum 16 mg/day).

In the event of grade 3 or 4 diarrhea, the following supportive measures are allowed: hydration, octreotide, and antidiarrheals.

If diarrhea is severe (requiring intravenous rehydration) and/or associated with fever or severe neutropenia (grade 3 or 4), broad-spectrum antibiotics must be prescribed. Patients with severe diarrhea or any diarrhea associated with severe nausea or vomiting **should be hospitalized** for intravenous hydration and correction of electrolyte imbalances.

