8.0 Dosage Modification Based on Adverse Events

Strictly follow the modifications in this table for the first **two** cycles, until individual treatment tolerance can be ascertained. Thereafter, these modifications should be regarded as guidelines to produce mild-to-moderate, but not debilitating, side effects. If multiple adverse events are seen, administer dose based on greatest reduction required for any single adverse event observed. Reductions or increases apply to treatment given in the preceding cycle and are based on adverse events observed since the prior dose.

ALERT: ADR reporting may be required for some adverse events (See Section 10)

8.1 Dose Levels (Based on Adverse Events in Tables 8.2 and 8.3), if applicable – This is potentially different information than what is found in the tables in Section 7.0.

Dose		
Level	Encorafenib	Binimetinib
0	450 mg	45 mg
-1	300 mg	30 mg
-2	225 mg	15 mg

* Dose level 0 refers to the starting dose.

The lowest recommended dose level of encorafenib is 225 mg QD and the lowest recommended dose level of binimetinib is 15 mg BID. When the AE that resulted in a dose reduction improves to and remains stable at the patient's baseline level for a minimum of 14 days, the dose can be re-escalated to the next dose level at the discretion of the Investigator, provided there are no other concomitant toxicities that would prevent drug re-escalation. There is no limit to the number of times the patient can have their dose reduced or re-escalated, however:

- No dose re-escalation of encorafenib is allowed after a dose reduction due to prolonged QTcF ≥ 501 msec
- No dose re-escalation of binimetinib is allowed after a dose reduction due to LVEF dysfunction
- No dose re-escalation of binimetinib or encorafenib is allowed after a dose reduction due to retinal toxicity ≥ Grade 2.
- If binimetinib is withheld, consider reducing encorafenib to a maximum dose of 300 mg daily until binimetinib is resumed.

Please refer to Dose Modification Table for recommended dose modifications for encorafenib and/or binimetinib, if applicable, based on the occurrence of treatment-related AEs.

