10.53 Baseline and Adverse Events Evaluations

The following pre-treatment symptoms/conditions are to be graded at baseline and adverse events are to be graded at each evaluation using CTCAE v5.0 grading.

System Organ Class (SOC)	Adverse event/Symptoms	Baseline	Each evaluation
Eye disorders	Blurred vision	Х	Х
	Flashing lights	Х	Х
	Floaters	Х	Х
	Retinal vascular disorder	Х	Х
Investigations	Ejection fraction decreased	Х	Х
Musculoskeletal	Arthralgia	Х	Х
and connective	Myalgia	Х	Х
tissue disorders			
Skin and	Photosensitivity	Х	Х

subcutaneous tissue disorders	Rash acneiform Rash maculo-papular	X X	X X
General disorders and administration site conditions	Fatigue	X	Х
Gastrointestinal disorders	Diarrhea	# stools per day	Х

10.54 **Case Report Forms** - Academic and Community Cancer Research United (ACCRU)

Submit the following AEs not specified in Section 10.5 (paper or electronic, as applicable)

10.541 Grade 2 AEs deemed *possibly*, *probably*, *or definitely* related to the study treatment or procedure.

- 10.542 Grade 3 and 4 AEs regardless of attribution to the study treatment or procedure.
- 10.543 Grade 5 AEs (Deaths)
 - 10.5431 Any death within 30 days of the patient's last study treatment or procedure regardless of attribution to the study treatment or procedure.
 - 10.5432 Any death more than 30 days after the patient's last study treatment or procedure that is felt to be at least possibly treatment related must also be submitted as a Grade 5 AE, with a CTCAE type and attribution assigned.
- 10.55 Late occurring adverse events are any adverse event that occurs during Event Monitoring reporting period. These are reported in compliance with Section 4.0 and Section 18.0.
- 10.56 Monthly Report: Research Coordinating Center will provide Array BioPharma, Inc. with accrual report on a monthly basis.

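### The binimetinib cardiac row in Table 8.3 acts at Grade 1 and at Grade 3-4 but has no Grade 2 entry, and no row names the LVEF term that Section 10.53 has sites grade

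*Combined protocol and SAP*

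**What the plan says.** Table 8.3 (Recommended Binimetinib Dose Modifications) has one row under Cardiac Disorders, headed "Heart Failure and Left ventricular systolic dysfunction". It contains two grade entries:

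- **Grade 1:** "Withhold binimetinib for up to 4 weeks, evaluate LVEF every 2 weeks". Binimetinib may then restart at a lower dose if LVEF is not below the lower limit of normal, "Absolute decrease from baseline is 10% or less", and the patient has no symptoms. If LVEF has not recovered in 4 weeks, the drug stops for good.
- **Grade 3-4:** "Permanently discontinue binimetinib. Closely monitor LVEF until resolution or up to 16 weeks".

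Section 8.0 sets the status of the table: "Strictly follow the modifications in this table for the first" two cycles. After that it becomes guidance.

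Section 10.53 has sites grade "Ejection fraction decreased" at baseline and at each evaluation, under the system organ class Investigations. The Investigations block of Table 8.3 names ALT/AST increased and CPK increased, and then has "Investigations-Other, specify". For a recurrent Grade 2 or a first Grade 3, that last row orders a hold of up to 4 weeks and then: "If improves to Grade 0-1 or to pretreatment/baseline levels, resume at reduced dose".

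Footnote 9 of the Section 4.0 test schedule places ECHO/MUGA at screening, Cycle 2 Day 1, every 12 weeks after that, and end of treatment.

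**The concern.** A dose-modification row should give an order at every grade from the lowest at which it acts. This one acts at Grade 1, is silent at Grade 2 and acts again at Grade 3-4. A site that obeys it literally interrupts the drug for the milder event and has no instruction for the worse one. The protocol itself treats this toxicity as important: Section 15.17 lists decreased ejection fraction among the very common binimetinib effects, Section 4.0 schedules repeated LVEF imaging, and Section 8.1 bars binimetinib re-escalation after a reduction for LVEF dysfunction.

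The second matter is how a site finds the right row. Table 8.3 is arranged by system organ class. The term that sites are told to grade sits under Investigations, while the only row written about LVEF sits under Cardiac Disorders. No text connects the two. What is at stake is patient safety and consistent handling across sites; no effect on the response endpoint has been shown.

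**Working it through.** The plan gives no figure to reproduce, so the check is a side-by-side reading.

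**Step 1. Grade by grade, binimetinib, Table 8.3**

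| Event | Cardiac row | Investigations catch-all row |
|---|---|---|
| Grade 1 | Hold up to 4 weeks; restart lower if three conditions are met, otherwise stop | No entry |
| First Grade 2 | **No entry** | **No entry** (the row begins at recurrent Grade 2) |
| Recurrent Grade 2 | No entry | Hold up to 4 weeks; restart lower if improved |
| First Grade 3 | Permanent stop | Hold up to 4 weeks; restart lower if improved, otherwise stop both drugs |
| First Grade 4 | Permanent stop | Permanent stop, or hold up to 4 weeks and restart lower if improved |

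**Step 2. Does another passage fill the first Grade 2 cell?**

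- Table 8.2 (encorafenib) has no cardiac row.
- Section 8.1 mentions LVEF only to bar re-escalation after a reduction. It gives no action by grade.
- The ALT/AST rows point to an entry for other adverse reactions, but no row in either table carries that name, so there is no stated general fallback.
- The Section 8.0 instruction for several simultaneous events is to take the largest reduction that any one of them requires. It adds nothing where no reduction is listed.

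Nothing fills the cell under either row.

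**Step 3. Is this just a row that starts at a higher grade?** No. The pneumonitis row, for example, starts at Grade 2 and then covers Grade 3 and Grade 4. The cardiac row is the only one in Tables 8.2 and 8.3 that acts at one grade, is silent at the next and acts again above it.

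**Step 4. Does the gap fall inside the binding window?** Cycles are 28 days, so the first two cycles run from Day 1 to Day 2 × 28 = 56. Cycle 2 Day 1 is Day 28 + 1 = 29. The first scheduled on-treatment ECHO/MUGA therefore falls while the table must be followed strictly, assuming no delay that moves the cycle.

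**Step 5. Where does the Section 10.53 term go?** No row of Table 8.3 names it, and no text assigns it to either row. The cardiac row is written throughout in LVEF terms: repeat LVEF checks, comparison with the lower limit of normal, change from baseline, continued LVEF monitoring. That makes it the natural home. A site that goes by system organ class could still arrive at the catch-all row, and the table in Step 1 shows that the first Grade 3 order there differs.

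**The case against.** The best defence has four parts.

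1. **The gap rests on one label.** The text was read from PDF by a program, and single characters are misread elsewhere (two exclusion-criterion letters in Section 3.3, for instance). The Grade 1 label could be such a misreading. This stands as a reason to check the source document. Nothing in the row suggests a lost line, and the available text has the gap.

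2. **The strict period is short.** The table binds for two cycles and then guides, and only one on-treatment LVEF assessment is scheduled in that time. This limits the exposure but does not remove it, and a guideline with a missing middle grade remains a poor guideline.

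3. **The two rows do not truly conflict.** A reader might infer that the same Grade 3 LVEF fall carries two incompatible orders. The documents do not support that. They never place the Section 10.53 term in the catch-all row, Section 10.1 treats each CTCAE term as one specific event, and the cardiac row is written about LVEF. If a site recorded both a cardiac and an Investigations term, the largest-reduction instruction in Section 8.0 would point to the stricter order. This objection stands: the supportable statement is that the term is unmapped.

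4. **Re-escalation does not turn on coding.** A reader might also infer that the Section 8.1 bar on re-escalation would apply or not according to the row used. It depends on the reason for the reduction, not on the row or coded term, so that inference fails too.

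**Conclusion.** The Grade 2 gap holds under either reading of which row governs an LVEF fall, and it must be fixed. A stated safety rule, followed as written in the period when it is binding, orders a hold for the milder event and nothing for the worse one. The missing link between "Ejection fraction decreased" and a row is a lesser, real ambiguity.

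The size is one grade of four without an action, plus one graded term without an assigned row. The number of patients affected is unknown. A reader might take the Section 15.17 band of 10% or more for decreased ejection fraction and compute 0.10 × 26 = 2.6, about 3 evaluable patients. That band covers all grades, while the gap concerns Grade 2 and the ambiguity mainly Grade 3, and the documents give no grade mix. The same section puts left ventricular dysfunction, the term closest to the row heading, at 0.1% to below 1%, which gives fewer than 0.01 × 26 = 0.26 patients. Neither figure estimates how often the defect would bite.

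The conclusion assumes that the Grade 1 and Grade 3-4 labels match the source document.

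**What to change.** The sponsor should:

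1. check the Grade 1 label of the cardiac row in Table 8.3 against the source document;
2. reconcile that row so that every grade is covered without a gap;
3. state which row of Table 8.3 governs events graded under Section 10.53 as "Ejection fraction decreased".

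The choice of action at each grade is the sponsor's, and none is proposed here. The cost is one table amendment and a memo to sites. No added assessment is needed, because LVEF is already measured on the Section 4.0 schedule.

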9.5 Permitted Concomitant Therapy Requiring Caution and/or Action

Encorafenib is a reversible inhibitor of CYP1A2, CYP2B6, CYP2C8, CYP2C9, CYP3A4 and UGT1A1. It is also a time-dependent inhibitor of CYP3A4, and induced CYP2B6, CYP2C9 and CYP3A4 in human primary hepatocytes. Permitted medications to be used with caution in this study include those that are sensitive substrates of CYP1A2, CYP2B6, CYP2C9, CYP2C9, CYP3A4, and UGT1A1 or those substrates that have a narrow therapeutic index.

There is a potential for encorafenib to induce CYP3A4, which may reduce the effectiveness of hormonal contraception methods. Therefore, the use of at least 1 form of non-hormonal contraception is required for females of childbearing potential during participation in this study. Caution should be used in participants receiving concomitant treatment with other drugs that are substrates of CYP3A4 as the efficacy of these drugs could be reduced when administered with encorafenib.

Encorafenib has been identified in vitro to be metabolized by CYP3A4 and to a lesser extent by CYP2C19. The use of strong inhibitors of CYP3A4 is prohibited. Concomitant use of moderate CYP3A4 inhibitors while on study should be avoided. If use of moderate CYP3A4 inhibitors is unavoidable and no alternatives are available, short-term use (\leq 30 days) is permitted with accompanying dose reduction to one-half of the encorafenib dose prior to use of moderate CYP3A4 inhibitors (or as close as can be achieved without exceeding the target dose). The encorafenib dose that was taken prior to initiating the CYP3A4 inhibitor may be resumed after the inhibitor has been discontinued for 3 to 5 elimination half-lives. Strong inhibitors of CYP2C19 should be used with caution when co-administered with encorafenib. Use of moderate and strong inducers of CYP3A4 is prohibited.

In vitro data showed that encorafenib is a substrate of the transporter P-gp. Thus, drugs that are known to inhibit or induce P-gp should be used with caution. Encorafenib is also a potent inhibitor of the renal transporters, OAT1, OAT3 and OCT2, and the hepatic transporters OATP1B1 and OATP1B3. The co-administration of drugs that are known to be sensitive or narrow therapeutic index substrates of OAT1, OAT3, OCT2, OATP1B1 or OATP1B3 should be used with caution.

In vitro, binimetinib has been identified to be primarily metabolized by glucuronidation through UGT1A1. Binimetinib has also been shown to be a substrate of P-gp and BCRP. It is advised that inhibitors and inducers of UGT1A1, P-gp or BCRP transporters should be taken with caution when co-administered with binimetinib.

For a listing of examples of substrates, inhibitors and inducers to be used with caution, please consult with the FDA website: Drug Development and Drug Interactions: Table of Substrates, Inhibitors and Inducers. Note that this list is not exhaustive.

Investigators should use caution when administering encorafenib and binimetinib with concomitant medications with a known, conditional or possible risk to prolong the QT interval and/or induce TdP. Subjects receiving such medications must be carefully monitored for potentiation of toxicity due to any individual concomitant medication, and may require dose titration of the concomitant medication. See the CredibleMeds[®] website for examples: Combined List of Drugs That Prolong QT and/or cause Torsades de Pointes (TDP). Note that this list is not exhaustive.

9.6 Prohibited Concomitant Therapy

Concomitant strong systemic CYP3A4 inhibitors and strong or moderate systemic CYP3A4 inducers are likely to significantly increase or decrease encorafenib exposure, respectively, and thus should not be used during this study.

